### 12.6.3. Safety

Adverse Events
Duration of AE

 
Calculated as the number of [days] from AE Start Date to AE Stop Date:           
 
○ AE Start Date = Missing → Elapse Time = Missing
 
○ AE Stop Date = Missing → Elapse Time = Missing
 
○ Otherwise → Elapsed Time = AE Stop Date – AE Start Date + 1
 
 
 

Extent of Exposure

 
Number of weeks of exposure to study drug will be calculated based on the formula: Duration of Exposure in Weeks = [last dose date – first dose date + 1] /7
 
The cumulative dose will be based on the formula: Cumulative Dose = Sum of (the actual dose administered during each infusion)
 
The infusion dose intensity is the cumulative dose divided by the number of 3-week periods (cycles) across the entire treatment period.
 
For GSK3745417: Q1W: Dose intensity = Cumulative Dose/((last dose date – first dose date + 7)/21) Q3W: Dose intensity = Cumulative Dose/((last dose date – first dose date + 21)/21)
 
For dostarlimab:           
 
If a participant had <=4 doses of dostarlimab in total: Dose intensity = Cumulative Dose/ (last dose date – first dose date + 21)/21
 
If a participant had >4 doses of dostarlimab in total: Dose intensity = Cumulative Dose/ (last dose date – first dose date + 42)/21
 
 
 

Corrected QT Intervals

When not entered directly in the eCRF, corrected QT intervals using Fredericia's (QTcF) formula will be calculated, in msec, using QT and the RR interval:
 $QTcF = QT / \sqrt{3} \sqrt{RR / 1000}$

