### 8.1. Extent of Exposure

[figure not shown]
Extent of exposure will be summarized separately for GSK3745417 and dostarlimab.

Two summaries of exposure to study treatment will be produced for GSK3745417 and one summary table will be produced for dostarlimab. In the first expose table for GSK3745417 and for the exposure table for dostarlimab, the crossover cohorts will be included as separate cohorts, as per the standard approach. In the second exposure table for GSK3745417, the crossover information will be included in the display but will be included in the original monotherapy cohort (to summarise the total exposure to GSK3745417 across the monotherapy and crossover periods). In all exposure summaries, the following information will be included: dose intensity, time on study and cumulative actual dose.

The cumulative actual dose is the sum of the actual dose administered during each infusion for a participant throughout the period (GSK3745417 exposure table 1) or throughout the study (GSK3745417 exposure table 2 and dostarlimab exposure table). The cumulative actual dose will be summarized with mean, standard deviation, median, minimum, and maximum and will be categorised for GSK3745417 with the following categories: CCI

A cycle is defined as 21 days for both Parts 1A and 2A CCI. For GSK3745417, the number of cycles is defined as:

CCI

- If a participant had  $\leq 4$  doses of dostarlimab in total:  
$$(\text{last dose date} - \text{first dose date} + 21)/21$$
- If a participant had  $> 4$  doses of dostarlimab in total:  
$$(\text{last dose date} - \text{first dose date} + 42)/21$$

The dose intensity is calculated by 3-week periods (cycles) as the cumulative actual dose divided by the number of cycles. The dose intensity (mg/cycle) will be summarized using mean, median, standard deviation, minimum, and maximum.

The time on study treatment (weeks) will be calculated for each participant as (last dose date – first dose date + 1) /7. See [Table 2](#) for how treatment first and last dose dates are derived for the monotherapy (Part 1A) and crossover cohorts in the three exposure tables. The time on study treatment (weeks) will be summarized with mean, standard deviation, median, minimum, and maximum and will also be categorised into the following categories: <=10 weeks, > 10 weeks to 20 weeks, > 20 weeks to 30 weeks, >30 weeks to 40 weeks and > 40 weeks.

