**Table 2 Treatment first and last dose dates for the monotherapy (Part 1A) and crossover cohorts in the three exposure tables**

Table	Part 1A: Monotherapy	Crossover
GSK3745417 (Exposure table 1: Separate crossover cohorts)	Start: Monotherapy first dose date End: Monotherapy last dose date	Start: Combination (crossover) first dose date End: Combination (crossover) last dose date
GSK3745417 (Exposure table 2: Crossover information displayed in monotherapy cohorts)	Start: Monotherapy first dose date End: Combination (crossover) last dose date	N/A
Dostarlimab (Separate crossover cohorts)	N/A	Start: Combination (crossover) first dose date End: Combination (crossover) last dose date

Extent of exposure to GSK3745417 and dostarlimab will be listed separately, including dose intensity (mg/cycle, displayed at the participant level), start date and time of exposure, study day and period day with respect to start date, stop date and time of exposure, study day and period day with respect to stop date, scheduled dose (mg), actual dose (mg), and cumulative actual dose (mg). For GSK3745417, crossover information will be included in the listing by having two sets of rows per crossover participant: one set for GSK3745417 as monotherapy and one set for GSK3745417 as combination therapy (all will be included under the original monotherapy treatment cohort). There will also be an additional column in the listing for period (monotherapy vs. combination therapy). For dostarlimab, the crossover cohorts will be included (as per the standard approach).

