### 8.1.1. Dose Modifications

A summary listing of overall exposure and dose modification will also be created, including component (GSK3745417 or dostarlimab), time on study treatment (weeks), dose intensity (mg/cycle), cumulative dose (mg), and a dose modification summary. Dose modification will be summarized by total number of dose delays, missed doses, dose reductions, dose escalations, infusions interrupted but completed, and infusions stopped early and not completed. Note that if a participant crosses over to combination therapy, then all dose exposure and modifications

from both the monotherapy and combination periods will be included in a single GSK3745417 component row.

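### Section 12.6.3 omits the bracket around the number of cycles in both dostarlimab dose-intensity formulas, so as printed they give 1/441 of the intended value (minor)

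*SAP*

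**What the plan says.** Section 8.1 (Extent of Exposure) sets a cycle at 21 days. For dostarlimab it counts cycles as the days from first to last dose, plus 21 (four doses or fewer) or plus 42 (more than four doses), all divided by 21. It then states: "The dose intensity is calculated by 3-week periods (cycles) as the cumulative actual dose divided by the number of cycles". The unit is fixed as well: "The dose intensity (mg/cycle) will be summarized using mean, median, standard deviation, minimum, and maximum".

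Section 12.6.3 (Safety, Extent of Exposure) repeats the definition in words: "The infusion dose intensity is the cumulative dose divided by the number of 3-week periods (cycles) across the entire treatment period". Below it stand four formulas:

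- The two GSK3745417 formulas enclose the number of cycles in its own bracket. The Q3W line reads "Dose intensity = Cumulative Dose/((last dose date – first dose date + 21)/21" and then closes the outer bracket. The Q1W line has the same structure with 7 days added.
- The two dostarlimab formulas have no such bracket. For more than four doses the line is "Dose intensity = Cumulative Dose/ (last dose date – first dose date + 42)/21". For four doses or fewer it is the same with 21 in place of 42.

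The footnotes specified for Tables 3.21 and 3.22 in Section 12.10.5 again define dose intensity as cumulative actual dose over number of cycles.

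**The concern.** Division runs from left to right, including in SAS and R, the software named in Section 12.5.1. Without the bracket, the dostarlimab lines divide the cumulative dose by a number of days and then divide again by 21. The definition requires division by the number of cycles, which is days divided by 21. The printed result is therefore not in mg/cycle.

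Section 12.6.3 belongs to the appendix of derivations, and it is the only place where the dostarlimab formula is written out in one line, so a programmer could code it as it stands. The quantity is displayed in three places:

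- Table 3.21 (dostarlimab exposure).
- Table 3.22, whose content under Section 8.1.1 includes "time on study treatment (weeks), dose intensity (mg/cycle), cumulative dose (mg), and a dose modification summary".
- The dostarlimab exposure listing (Listing 11), because Section 8.1 says that exposure to each drug "will be listed separately, including dose intensity (mg/cycle, displayed at the participant level".

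**Working it through.** The SAP states no numerical dose intensity, so there is no figure to reproduce. The check compares the two forms of the formula.

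**Inputs**

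- C = cumulative dostarlimab dose in mg.
- D = last dose date minus first dose date, in days.
- k = 21 for four doses or fewer, 42 for more than four (Sections 8.1 and 12.6.3).
- Schedule for the examples (Section 3.1): 500 mg every 3 weeks for the first four doses, then 1000 mg every 6 weeks.

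**Algebra**

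- Section 8.1: C / ((D + k)/21) = 21C / (D + k)
- Section 12.6.3 as printed: C / (D + k) / 21 = C / (21(D + k))
- Ratio of the first to the second: 21 x 21 = 441, whatever C, D and k are.

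**Examples**

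| Case | C | D | k | Cycles | Section 8.1 (mg/cycle) | As printed |
|---|---|---|---|---|---|---|
| One dose | 500 | 0 | 21 | 1 | 500/1 = 500 | 500/21/21 = 1.134 |
| Four doses, every 3 weeks | 2000 | 63 | 21 | 4 | 2000/4 = 500 | 2000/84/21 = 1.134 |
| Five doses, fifth 3 weeks after fourth | 3000 | 84 | 42 | 6 | 3000/6 = 500 | 3000/126/21 = 1.134 |
| Five doses, fifth 6 weeks after fourth | 3000 | 105 | 42 | 7 | 3000/7 = 428.6 | 3000/147/21 = 0.972 |

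The SAP does not state the interval between the fourth and fifth doses, so the last two rows show two assumed values. The ratio is 441 in every row.

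**Control.** The GSK3745417 formulas, which have the bracket, give the expected values. With an illustrative 1 mg dose, three weekly doses give 3/((14 + 7)/21) = 3 mg/cycle, and two doses three weeks apart give 2/((21 + 21)/21) = 1 mg/cycle. The fault lies only in the two dostarlimab lines.

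**The case against.** The strongest reply is that the SAP contains one rule and a slip of notation, not two competing rules. Section 8.1 gives the number of cycles for both dose groups, the definition in words stands just above the formulas, the neighbouring lines have the bracket, and the table footnotes repeat the rule. A programmer would have to overlook all of these and then accept about 1 mg/cycle for a drug given at 500 or 1000 mg. This stands, and it is why the point is minor. The printed lines are still wrong.

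Nothing inferential depends on the quantity. The primary endpoints are DLTs and adverse events, the secondary endpoint is GSK3745417 pharmacokinetics, and dose escalation uses DLT probabilities. Cumulative dose and time on treatment have their own formulas. This also stands.

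The brackets might have been lost when the PDF was converted to text; the QTcF formula in the same section is visibly distorted. That cannot be ruled out completely, but it is unlikely. Each dostarlimab line is plain text with balanced brackets, so an opening and a closing bracket would have to vanish from both lines while the GSK3745417 lines kept theirs. A look at the source file settles it.

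Finally, the specification of Listing 11 does not itself mention dose intensity. The link rests on the general text of Section 8.1, which covers the exposure listings of both drugs, and that is sufficient.

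**Conclusion.** The point holds as a minor specification error. Both dostarlimab dose-intensity formulas in Section 12.6.3 disagree with Section 8.1, with the definition in their own cell and with the footnotes to Tables 3.21 and 3.22. If coded literally, every dostarlimab dose intensity would be 1/441 of its intended value, about 1.13 where 500 mg/cycle is meant. This is the size of the error if the lines are followed as printed, not an expected error in the report: a value near 1 mg/cycle would probably be noticed. The conclusion assumes normal operator order and that the text reproduces the source file faithfully.

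**What to change.** In Section 12.6.3, put the number of cycles in its own bracket, as in the GSK3745417 lines and in agreement with Section 8.1:

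- Four doses or fewer: Cumulative Dose / ((last dose date - first dose date + 21)/21)
- More than four doses: Cumulative Dose / ((last dose date - first dose date + 42)/21)

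Then confirm that the programs for Tables 3.21 and 3.22 and Listing 11 use this form. A single participant with four 500 mg doses at three-week intervals is enough as a test and must return 500 mg/cycle. The cost is one pair of brackets in each of two lines and a check of three programs. Doses, schedule, data collection and design are untouched.

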### 12.6.4. Crossover

The date (and time, where applicable) of crossover is defined as the date (and time) of the first dose of combination therapy for participants who were initially assigned monotherapy.

## 12.7. Appendix 7: Reporting Standards for Missing Data

### 12.7.1. Premature Withdrawals

Element	Reporting Detail
General	
 
Participants will be considered to have completed the DLT portion of the study if they complete screening assessments and receive at least 1 study treatment and experience a DLT during the 21 or 29-day DLT observation period or complete the DLT observation period.
 
A participant will be considered to have completed the study if the site indicated on the eCRF that they did not discontinue the study before completing the follow up. 
 
Under Protocol Amendment 7, the required follow-up period is until 90 days after last dose, starting subsequent anti-cancer therapy or dying. Participants who are in follow-up at the time of Protocol Amendment 7 and have been followed for at least 90 days are considered as having completed the follow-up period.
 
Prior to Protocol Amendment 7, the required follow-up period was 2 years from first dose (or until death).
 
 
 
A participant will be considered to have withdrawn from the study if (1) the participant has not died and is lost to follow-up, (2) the participant has withdrawn consent, (3) at the investigator's discretion is no longer being followed, or (4) the study is closed/terminated.
 
If a participant withdraws from the study before completion of the DLT period for reasons other than DLT, the participant will not be counted as DLT evaluable and will be replaced.
 
All available data from participants who were withdrawn from the study will be listed and all available planned data will be included in summary tables and figures, unless otherwise specified.
 
If PACT is initiated, participants who transition to PACT will be considered as ongoing in the study.
 

### 12.7.2. Handling of Missing Data

Element	Reporting Detail
General	
 
Missing data occurs when any requested data is not provided, leading to blank fields on the collection instrument: 
 
These data will be indicated using a “blank” in participant listing displays. Unless all data for a specific visit are missing in which case the data is excluded from the table.
 
Answers such as “Not applicable” and “Not evaluable” are not considered to be missing data and should be displayed as such.
 
 
 

Element	Reporting Detail
Outliers	

• Any participants excluded from the summaries and/or statistical analyses will be documented along with the reason for exclusion in the clinical study report.

**12.7.2.1. Handling of Missing and Partial Dates**

Element	Reporting Detail
General	Partial dates will be displayed as captured in participant listing displays. <small>CC1</small>
Adverse Events	

**CONFIDENTIAL**

Element	Reporting Detail
	CCI
Concomitant Medications/ Medical History	
Prior Anti-cancer Systemic	

Element	Reporting Detail
Therapy/ Radiotherapy/ Surgical Procedures	CCI
Follow-up Anti-cancer Systemic Therapy (as adjudicated by the clinical team)/Cancer related Surgical Procedures for Efficacy Evaluation (BOR) and TEAE definition	
Other Follow- up Anti-cancer Systemic Therapy/ Radiotherapy/ Non-cancer related Surgical Procedures	
On-treatment Radiotherapy	CCI

#### 12.7.2.2. Handling of Missing Dates in terms of crossover

This sub-section describes which period (that is, monotherapy or crossover combination therapy) events should be included in for crossover participants when either the start or end date of the event is missing.

#### Concomitant medication

Note that the only concomitant display to be produced is a listing.

Concomitant Medication Start Date	Concomitant Medication End Date	Cohort Inclusion Rule
Before crossover	Before crossover	Include in monotherapy cohort only
Before crossover	After crossover	Include in both monotherapy and crossover cohort
Before crossover	Missing	Include in both monotherapy and crossover cohort
After crossover	After crossover	Include in crossover cohort only
After crossover	Missing	Include in crossover cohort only
Missing	Before crossover	Include in monotherapy cohort only
Missing	After crossover	Include in both monotherapy and crossover cohort
Missing	Missing	Include in both monotherapy and crossover cohort

## 12.8. Appendix 8: Values of Potential Clinical Importance

To identify values of potential clinical importance, CTCAE version 5.0 will be used to assign grades for laboratory parameters including clinical chemistry, hematology, liver function tests and vital signs (blood pressure, temperature). For urinalysis, a participant is considered to have urinalysis results of PCI, if there is an increase in Protein or an increase in Occult Blood results during the study, or if microscopy is performed.

Reference ranges for all laboratory parameters collected throughout the study are provided by the laboratory. A laboratory value that is outside the reference range is considered either high abnormal (value above the upper limit of the reference range) or low abnormal (value below the lower limit of the reference range). Note: a high abnormal or low abnormal laboratory value is not necessarily of clinical concern. The laboratory reference ranges will be provided on the listings of laboratory data. Clinical laboratory test results outside of the reference range will be flagged in the listings.

### 12.8.1. ECG

ECG Parameter	Units	Clinical Concern Range		
		Lower	Upper	
Absolute				
Absolute QTcF Interval	msec	Grade 1	$\geq 450$	$< 481$
		Grade 2	$\geq 481$	$< 501$
		Grade 3	$\geq 501$	
Change from Baseline				
Increase from Baseline QTcF	msec		$> 30$	$\leq 60$
	msec	Grade 3	$> 60$	

### 12.8.2. Vital Signs

Vital Sign Parameter (Absolute)	Units	Clinical Concern Range		
		Lower	Upper	
Systolic Blood Pressure	mmHg	Grade 1	$\geq 120$	$< 140$
	mmHg	Grade 2	$\geq 140$	$< 160$
	mmHg	Grade 3	$\geq 160$	
Diastolic Blood Pressure	mmHg	Grade 1	$\geq 80$	$< 90$
	mmHg	Grade 2	$\geq 90$	$< 100$
	mmHg	Grade 3	$\geq 100$	
Heart Rate	bpm	L/H	$< 60$	$> 100$
Temperature	Degrees C	L/H	$\leq 35$	$\geq 38$

## 12.9. Appendix 9: Abbreviations & Trademarks

### 12.9.1. Abbreviations

Abbreviation	Description
AE	Adverse Event
AESI	Adverse Event of Special Interest
ALT	Alanine Aminotransferase
AST	Aspartate Transferase
AUMC	Amsterdam University Medical Centers
BLRM	Bayesian Logistic Regression Model
BOR	Best Overall Response
BP	Blood Pressure
BUN	Blood Urea Nitrogen
CBC	Complete Blood Count
CI	Confidence Interval
CPMS	Clinical Pharmacology Modelling & Simulation
CR	Complete Response
CRS	Cytokine Release Syndrome
CSR	Clinical Study Report
CTCAE	Common Terminology Criteria for Adverse Events
DBF	Database Freeze
DBR	Database Release
DEM	Dose Escalation Meeting
DLT	Dose Limiting Toxicity
DM	Data Management
DP	Decimal Place
ECG	Electrocardiogram
ECOG	Eastern Cooperative Oncology Group
eCRF	Electronic Case Report Form
GSK	GlaxoSmithKline
HPV	Human Papillomavirus
IB	Investigator Brochure
IDSL	Integrated Data Standards Library
irAE	Immune-Related Adverse Event
IRR	Infusion-Related Reaction
LLQ	Lower Limit of Quantification
LVEF	Left Ventricular Ejection Fraction
MSI	Microsatellite Instability
MTD	Maximum Tolerated Dose
NA	Not Applicable
NE	Not Evaluable
NQ	Non-Quantifiable
CCI	
PACT	Post Analysis Continuation of Treatment
PCI	Potential Clinical Importance

Abbreviation	Description
PD	Progressive Disease
PK	Pharmacokinetic
PK/PD	Pharmacokinetics/Pharmacodynamics
PR	Partial Response
PT	Preferred Term
Q1W	Every 1 week
Q3W	Every 3 weeks
Q6W	Every 6 weeks
QTc	QT Correction
QTcF	Fridericia's QT Correction
RAP	Reporting & Analysis Plan
RBC	Red Blood Cells
RECIST	Response Evaluation Criteria in Solid Tumours
RP2D	Recommended Phase 2 Dose
S&P	Statisticians and Programming
SAC	Statistical Analysis Complete
SAE	Serious Adverse Event
SD	Stable Disease
SDTM	Study Data Tabulation Model
SERM	Safety Evaluation and Risk Management
SOC	System Organ Class
StD	Standard Deviation
TDV	Treatment Discontinuation Visit
TEAE	Treatment-Emergent Adverse Event
TLF	Table, Listing, Figure
TMF	Trial Master File
WBC	White Blood Cells

### **12.9.2. Trademarks**

Trademarks of the GlaxoSmithKline Group of Companies
HARP

Trademarks not owned by the GlaxoSmithKline Group of Companies
SAS
WinNonLin

## 12.10. Appendix 10: List of Data Displays

### 12.10.1. Data Display Numbering

The following numbering will be applied for RAP generated displays:

Section	Tables	Figures
Study Population	1.1 to 1.n	1.1 to 1.n
Safety	3.1 to 3.n	3.1 to 3.n
Pharmacokinetic	4.1 to 4.n	4.1 to 4.n
Efficacy	6.1 to 6.n	6.1 to 6.n
Section	Listings	
ICH Listings	1 to 23	
Other Listings	24 to 25	

### 12.10.2. Mock Example Shell Referencing

Non IDSL specifications will be referenced as indicated and if required example mock-up displays provided in Section 12.10: Example Mock Shells for Data Displays.

Section	Figure	Table	Listing
Study Population	POP_Fn	POP_Tn	POP_Ln
Safety	SAFE_Fn	SAFE_Tn	SAFE_Ln
Pharmacokinetic	PK_Fn	PK_Tn	PK_Ln
Efficacy	EFF_Fn	EFF_Tn	EFF_Ln

### 12.10.3. Deliverables

Delivery	Description
IB	Investigator Brochure Update
DEM	Dose Escalation Meeting (Part 1A)
SAC	(CSR) Statistical Analysis Complete

#### Note for Programmers:

Analyses will be reported by actual treatment dose level received at first dosing, except PK analyzes where data will be summarized by the actual dose received for each visit.

Include dose levels from both Part 1A and Part 2A in all the displays unless otherwise stated. Include total for all the tables (except PK tables) and the total should be separate for Part 1A, Part 2A and Crossover (when included). It should not be combined unless otherwise stated. For all the summary tables, cluster all the dose levels within Part 1A and dose levels within Part 2A as provided in the mock shell. All listings will be sorted by Treatment, site ID, unique subject ID, subject ID and then by date and time, if applicable. Include treatment as a header in each

**CONFIDENTIAL**

page of the listing as provided in the mock shell. Include site ID, unique subject ID and subject ID in a stacked column for all the listings as provided in the mock shell.

Some listings were only produced statically for the IB and the data will be available to view in RAPIDO DV for the CSR SAC.

## CONFIDENTIAL

## 12.10.4. Study Population Tables

Study Population Tables					
No.	Population	IDSL / Example Shell	Title	Programming Notes	Deliverable
Subject Disposition					
1.1.	All Treated	ES8	Summary of Subject Status and Subject Disposition for the Study Conclusion Record	
Use sentence case for text in the template. Do not use upper case.
 
Split Part 1A into Part 1A Non-Crossover and Part 1A Crossover. Use the crossover cohorts in Part 1A Crossover.
 
Use reasons for study withdrawal from eCRF, not from the standard.
 
Participants are included in the “Ongoing: On study treatment” row if the reason for study discontinuation was “Protocol-defined stopping criteria” and the specify variable (upper case) contained both the strings “PACT” and “CONTINUING TREATMENT”.
 
Participants are included in the “Ongoing: In follow-up” row if the reason for study discontinuation was “Protocol-defined stopping criteria” and the specify variable (upper case) contained both the strings “PACT” and “90 DAY SAFETY FOLLOW-UP”.
	SAC

